**NCT Number 02473471**

**February 21, 2017**

## **MATERIAL AND METHODS:**

### **Trial design and any changes after trial**

#### **Commencement**

This study was a split mouth randomized clinical trial with a 1:1 allocation. Methods were not changed after trial initiation.

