### **Sample size calculation**

The sample size was calculated based on a type I error frequency of 5%. According to the power analysis and assuming a large effect size difference between groups (effect size= 0.8), the power analysis yielded 28 subjects per group at a conventional alpha level ( $p = 0.05$ ) and desired power ( $1 - \beta$ ) of 0.90, yielding a total sample size estimate of 56 subjects. All calculations were performed with the computer application G-Power .

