## **Secondary Outcomes**

Root resorption was evaluated, as a secondary outcome, using the periapical radiographs of the canines before canine retraction and after three months. One operator, using parallax technique made all digital periapical radiographs by the same X-ray machine (RXDC eXTend, Myray, Italy), set up at 7 mA, 60 kV with an exposure time of 0.32 second. DIGORA Optime digital imaging plate system with its phosphor plate films (Soredex, Finland) was used in this study. Intraoral XCP film holders were used (Dentsply Rinn, Elgin, USA). Root resorption was measured using DIGORA for Windows 2.8 software, (Soredex, Finland). All radiographs were calibrated by 15.63 pixels per mm according to the manufacturing instruction. Root resorption in millimeter (mm) was measured by the difference between root length at baseline (R1) and after three months (R2). The reference point was the midpoint of mesial and distal cementoenamel junction (CEJ). The root length was calculated from root apex to the midpoint of cementoenamel junction (CEJ).

Periodontal index and plaque index were also evaluated clinically in both upper

canines and second premolars before canine retraction and after three months according to Löe. Both pain intensity and interference were evaluated using Visual Analog Scale (VAS) from 0 to 10 Numeric Rate Scale (0= no pain, 10= severe pain). The participants filled out a questionnaire to assess the pain intensity immediately, after 1 hour, 12 hours, day 1, day 3, day 5 and day 7 following MOP intervention. Pain interference with daily life was assessed after MOP intervention on 1, 3, 5 and 7 days in which patients were asked to provide their subjective answers of pain during eating, pain awakened them at night, the feeling of discomfort and swelling on the surgical side. Numeric Rate Scale was also used to rate the level of satisfaction (0= not satisfied, 10= very satisfied) and easiness of MOP procedure (0= very easy, 10= very complicated). Moreover, the patients were asked if they were willing to repeat the procedure and recommend to a friend using categorical data (Yes or No). There were no changes to the outcome measures after trial commencement.

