#### **Statistical analysis (primary and secondary outcomes, subgroup analyses)**

Statistical analysis was accomplished using the Statistical Package for the Social Sciences computer software (SPSS 20.0, SPSS Inc., IL, USA). Probability values equal or less than 0.05 were considered significant. Independent sample t-tests were calculated to analyze the results of the primary outcome and secondary outcomes to compare the difference between MOP and control sides. Similarly, independent sample t-test was performed to compare the amount of root resorption before and after three months in MOP and control sides separately. Chi-square was used for analysis of categorical data including the willingness to repeat the procedure and recommend it to a friend. Descriptive statistics were used to describe the satisfaction and ease of the procedure.

Reliability coefficient (Cronbach's Alpha) was used to evaluate the reliability of measurements of primary outcomes. One examiner did all measurements, and all subjects were randomly selected. Six of 3D superimposed digital models had been chosen randomly. Superimpositions on the rugae area and canine displacement were measured twice within 2-week interval. Reliability coefficient (Cronbach's Alpha) was 0.95, showing excellent superimpositions and measurement agreement.

For intraoral measurements, intra-examiner reliability was done in the lower arch after reaching 0.019x0.025 stainless steel arch wire and teeth were in a passive state; all cases were non-extraction in the lower arch. Six of subjects were selected randomly, and measurements were done twice with the 2-week interval. Measurements were done from the upper mesial wings of the lower canine bracket to the upper distal wing of the lower second premolar bracket. Reliability coefficient (Cronbach's Alpha) was 1.00, indicating excellent measurement agreement.

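### Root resorption: the added before/after significance tests on each side do not test MOP, the plan does not say which analysis supports a conclusion, and all the t-tests treat paired data as independent

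*Combined protocol and SAP*

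**What the plan says.** The design is within-patient: "This study was a split mouth randomized clinical trial with a 1:1 allocation". The Secondary Outcomes section lists root resorption as a secondary outcome, taken from periapical radiographs of the canines, and defines it so: "Root resorption in millimeter (mm) was measured by the difference between root length at baseline (R1) and after three months (R2"). That is one change value per canine, in millimetres.

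The Statistical analysis section then provides two analyses that reach this outcome:

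- Independent-samples t-tests comparing MOP and control sides for the primary and the secondary outcomes. Root resorption is covered as a secondary outcome.
- In the next sentence, introduced as a similar step, independent-samples t-tests to "compare the amount of root resorption before and after three months in MOP and control sides separately".

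The significance rule is general: "Probability values equal or less than 0.05 were considered significant". No sentence says which of the two analyses carries a conclusion about MOP and root resorption.

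**The concern.** Three things are wrong with the second analysis, and one of them extends to the first.

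1. **It does not address MOP.** Each within-side test asks whether the canine root on that side became shorter during three months of retraction. Both canines are retracted, so shortening is possible on both sides whatever MOP does. Only the MOP-versus-control contrast uses the randomization of sides.
2. **It does not fit the outcome definition.** If resorption is R1 − R2, there is no amount of resorption before retraction to compare with an amount afterwards. The comparison must mean root length.
3. **The test ignores pairing.** R1 and R2 come from the same tooth. The between-side test has the same fault, because the two sides belong to the same patient. With positive correlation, both standard errors are too large.

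Root resorption is a harm outcome and the only outcome in the Secondary Outcomes section measured on radiographs. Two p-values side by side, without a rule on their use, leave room to read significance on one side only as harm or protection from MOP, and two non-significant results as no resorption. None of these follows. Inflated standard errors make the last misreading more likely.

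**Working it through.** **The plan's own figure.** The documents give no figure for the root-resorption tests. The nearest is the sample size: "the power analysis yielded 28 subjects per group at a conventional alpha level", "assuming a large effect size difference between groups (effect size= 0.8"), power "of 0.90, yielding a total sample size estimate of 56 subjects". The noncentral-t formula for two independent means at effect size 0.8, alpha 0.05 and power 0.90 gives 27.5, so 28 per group, one-sided, and 33.8, so 34 per group, two-sided. The stated 28 is therefore reproduced as a one-sided calculation; 28 per group has two-sided power 0.836. Below, 28 is used as the number per side. That is an assumption, since 56 subjects in a split-mouth trial could mean 28 patients or 56.

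**Other inputs.** Alpha 0.05 is from the Statistical analysis section; two-sided testing is assumed. The documents give no SD, expected shortening or correlation, so these are varied:

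- p: power of each within-side test
- c: between-side correlation of the changes
- r: correlation of R1 with R2 in the same tooth
- dz: true mean change divided by the SD of change, equal on both sides (no MOP effect)

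**Step 1. One-side-only significance in general.** P(exactly one side significant) = 2 × [p − P(both)].

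For independent sides this is 2p(1 − p): 9.5% at p = 0.05, 32% at 0.20, 50% at 0.50, 32% at 0.80 and 18% at 0.90. The maximum is at p = 0.50.

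For correlated sides at p = 0.50, the bivariate normal gives P(both) = 0.25 + arcsin(c)/(2π). At c = 0.5, 2 × [0.5 − (0.25 + 0.0833)] = 0.333. At c = 0.3 the result is 0.403, and at c = 0.7 it is 0.253.

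Simulation with correctly paired within-side tests at n = 28 agrees:

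| Per-side power | c = 0 | c = 0.5 | c = 0.8 |
|---|---|---|---|
| 5% (no shortening) | 9% | 8% | 6% |
| 20% | 32% | 24% | 15% |
| 50% | 50% | 34% | 21% |
| 80% | 32% | 23% | 15% |
| 90% | 18% | 13% | 9% |

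**Step 2. What ignoring the pairing does.** With equal variances σ², the unpaired SE is √(2σ²/n) and the paired SE is √(2σ²(1 − r)/n). The ratio is 1/√(1 − r): 1.41 at r = 0.5, 2.24 at r = 0.8 and 3.16 at r = 0.9. The same ratio holds between sides, with c in place of r.

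**Step 3. One-side-only significance with the planned unpaired before/after test.** Simulation, n = 28 per side, equal true change on both sides; ranges run from c = 0.5 to c = 0 in either order.

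| dz | r = 0.5 | r = 0.8 | r = 0.9 |
|---|---|---|---|
| 0 | about 1% | 0% | 0% |
| 0.385 | 24–36% | 3–4% | about 0% |
| 0.6 | 32–47% | 18–22% | 1–2% |
| 0.8 | 12–16% | 33–46% | 8–10% |
| 1.2 | about 0% | 8–9% | 34–44% |

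The unpaired test does not remove the pattern. It moves it to larger changes as r rises.

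**Step 4. The between-side comparison in the same simulations.** The paired test of MOP minus control in R1 − R2 rejects in about 5% of trials throughout. The planned unpaired test rejects in about 5% at c = 0 and about 0.7% at c = 0.5. As a rough check, an SE inflated by 1.41 moves the effective threshold from 1.96 to 1.96 × 1.41 = 2.77, and the two-sided normal tail beyond that is about 0.6%.

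**The case against.** The strongest reply is that the direct comparison is already planned. The sentence before the quoted one applies a MOP-versus-control test to all secondary outcomes, and root resorption is one of them. This stands. A reader of the quoted sentence alone might infer that side-by-side testing is the whole resorption analysis; the documents do not support that. The within-side tests are an addition.

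Second, nowhere does the plan say that significance on one side only will be taken as an MOP effect. This also stands. A reader might infer a decision rule of that kind, but the text contains none. The fair criticism is that the plan is silent on which analysis decides.

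Third, rates of a third to a half arise only with real shortening and intermediate per-side power. With the planned test, high before/after correlation and small change, the rate is close to zero. This stands too, so the full range has to be shown and no single figure can be called likely.

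Fourth, the clash with the outcome definition is loose wording, because root length at R1 and R2 is plainly meant. That is reasonable; it is an editorial correction.

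Fifth, it is legitimate to ask whether roots shortened on each side. It is, but an independent-samples test of R1 against R2 answers it with the wrong standard error. The mean per-tooth change with its confidence interval answers it directly.

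**Conclusion.** Wrong as written; minor to moderate, since the outcome is secondary. Three statements need no assumed figure: the within-side tests do not test MOP, the plan does not say which analysis supports a conclusion about MOP and resorption, and both analyses use an independent-samples test on paired data. That the standard errors are too large, and not too small, assumes positive correlation, which is plausible for two measurements of one tooth or two sides of one mouth.

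The size of the misreading risk is conditional. With equal true shortening on both sides, one-side-only significance could occur in about 0% to 50% of trials. The top of the range needs 50% per-side power and independent sides. The bottom occurs with the planned unpaired test when change is small and before/after correlation is about 0.9. It would be too strong to say that the trial is likely to produce this pattern, or that it would then report it as an MOP effect. The simulated figures rest on 28 per side, two-sided 5% tests, non-negative between-side correlation and the assumed values of r, c and dz.

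**What to change.** In the Statistical analysis section:

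- Replace the within-side independent-samples t-tests with the mean of R1 − R2 for each side and its 95% CI, computed from the per-tooth changes and labelled descriptive. This also removes the conflict with the outcome definition.
- State that any conclusion about MOP and root resorption rests only on the within-patient MOP-minus-control difference in R1 − R2, analysed as paired data and reported with its 95% CI.

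The change uses measurements that the plan already collects. The cost is that two within-side p-values are no longer reported.

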## Figure ligands

**Figure 1:** Micro-osteoperforations protocol

**Figure 2:** Diagrams of time events during the study

**Figure 3:** Clinical Micro-osteoperforations application. A, calibrated periodontal probe to locate the point of miniscrew insertion. B, Three bleeding points. C & D, First MOP application. E, 2nd MOP application. F, Three MOP were visible distal to canines. G, canine retraction by closed coil spring.

[figure not shown]
**Figure 4:** 3D digital superimposition. A, registration of 4 reference points at medial and lateral of third rugae area. B, performing registration and best-fit matching. C, best-fit color matching with blue the best match and red the worst.

**Figure 5:** Measurement of amount of canine retraction **on** 3D digital models. A, buccal view of upper left canines showing measurement tools on the Ceramill mind software. C, occlusal view of the canines showing the measurement tool. The canines in baseline model (Yellow color) and in the 3rd month model (purple color). B, the reference plane parallel to the bracket slots.

[figure not shown]

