## **Randomization (random number generation, allocation concealment, implementation)**

The intervention was randomly allocated to either right or left side with 1:1 allocation ratio. The randomization was accomplished using the permuted random block size of 2 with random generation function in Excel (Microsoft, Washington). Subsequently, the random sequence to either right or left were concealed in opaque envelopes and shuffled before the intervention to increase the unpredictability of the random allocation sequence. Each patient was asked to pick one sealed envelope to assign to the surgical intervention either on the right or the left side. Allocation concealment was aimed to prevent selection bias and protect the assignment sequence until allocation.

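### In the 3D-model measure, occlusal-plane rotation error in the rugae superimposition adds up in the MOP-minus-control difference, and the reported alpha does not show how repeatable that difference is

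*Combined protocol and SAP*

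**What the plan says.** The comparison is between the two sides of one mouth. Under Randomization: "The intervention was randomly allocated to either right or left side with 1:1 allocation ratio".

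Under Primary Outcomes, tooth movement is measured in two ways. One is a weekly caliper distance between canine and second premolar brackets. The other superimposes the models of months 1, 2 and 3 on the baseline model at the rugae and reads canine displacement. Under Figure ligands, the Figure 4 caption describes the superimposition as "registration of 4 reference points at medial and lateral of third rugae area", then best-fit matching. A colour map is used to judge the fit, with no numerical or angular limit. The 0.02 mm quoted under Primary Outcomes is the accuracy of the scanner, not of the registration.

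Under Statistical analysis, six superimposed models were chosen at random for a repeat: "Superimpositions on the rugae area and canine displacement were measured twice within 2-week interval". One Cronbach's alpha, 0.95, is reported and described as "showing excellent superimpositions and measurement agreement". No repeatability figure is given for the difference between sides. The planned comparison of MOP and control sides is an independent-samples t-test.

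**The concern.** A split-mouth comparison gains precision because errors common to both sides drop out of the difference. Rotation of the follow-up model in the occlusal plane is not such an error. As the procedure is described, each follow-up model is superimposed on baseline once and both canines are read from that superimposition, so the same rotation enters the two sides with opposite signs. Pairing cannot remove it.

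The reliability check concerns canine displacement, whereas the trial tests the difference between two canines. If rotation error is appreciable, the 3D-model contrast is less precise than an alpha of 0.95 suggests. Some of that lost precision could be recovered from scans that already exist.

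**Working it through.** **Inputs from the documents.** Split-mouth design; registration on four rugae points with best fit; alpha 0.95 from two readings of six models; 28 per group.

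**Inputs assumed, because the documents give none.** Canines 14 to 18 mm from the midline; rotation SD between 0.25 and 1 degree; a range of true right-left correlations.

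**The plan's own figures.** The sample size section states "the power analysis yielded 28 subjects per group at a conventional alpha level" for a standardised effect of 0.8 and power 0.90. For two independent means, a one-sided t-test needs 27.47, so 28 per group (power 0.905). A two-sided test needs 33.83, so 34; its power at 28 is 0.836. The 28 therefore reproduces as a one-sided calculation, and is used here only as n. The same section also gives a total of 56 subjects, so 56 patients is carried as an alternative. The alpha cannot be reproduced without the raw readings.

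**Geometry.** Let the follow-up model be turned by a small angle t (radians) in the occlusal plane about a centre at lateral position c. A point at lateral position x shifts anteroposteriorly by t(x − c). For canines at +w and −w the shifts are t(w − c) and t(−w − c), so the difference shifts by 2wt wherever the centre lies. About a midline centre the error in the difference is twice the single-canine error. Independent errors would give a factor of 1.41. Tilt about the transverse axis moves both canines alike and cancels.

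**Size.** One degree is 0.01745 radian. SE = difference error / √28 for one superimposition, and / √56 for the mean of two with independent errors.

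| Rotation SD | w (mm) | Each canine (mm) | Difference (mm) | SE, one | SE, mean of two |
|---|---|---|---|---|---|
| 0.25° | 17 | 0.074 | 0.148 | 0.028 | 0.020 |
| 1° | 14 | 0.244 | 0.489 | 0.092 | 0.065 |
| 1° | 16 | 0.279 | 0.559 | 0.106 | 0.075 |
| 1° | 18 | 0.314 | 0.628 | 0.119 | 0.084 |

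With 56 patients every SE is divided by √2.

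**What alpha 0.95 implies.** Two readings give a single-reading reliability r = 0.95 / (2 − 0.95) = 0.905. With true right-left correlation ρ and error correlation e, reliability of the difference = r(1 − ρ) / [r(1 − ρ) + (1 − r)(1 − e)].

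- ρ = 0.5: 1.00 if error is fully shared (e = 1), 0.83 if independent (e = 0), 0.70 if opposite (e = −1).
- ρ = 0.8: 1.00, 0.66 and 0.49.

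The same alpha is compatible with all of these. Its 95% interval is also wide: 0.64 to 0.99 if six readings were used, 0.83 to 0.99 if twelve canines were counted.

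**Is 1 degree plausible?** A simulated rigid fit on four points alone (assumed at ±3 and ±10 to 13 mm from the midline, point error SD 0.1 to 0.3 mm in each model) gave rotation SDs of 0.43 to 1.64 degrees. It leaves out surface best fit, which could reduce them. In that simulation tilt dominated and right-left errors correlated at 0.85 to 0.91, so single-canine reliability can mislead about the difference in either direction.

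**Planned test.** If rotation contributes variance s² to each canine, the true difference carries 4s². The independent t-test ignores the negative covariance and counts 2s².

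**The case against.** The strongest objection is that the decisive quantity, the rotation error, is nowhere stated and may be small. The four points are medial and lateral on the third rugae, so two of them are lateral, and a wider base resists rotation. Best-fit matching follows, and a colour map checks it. At 0.25 degree, averaging two superimpositions lowers this component's SE only from 0.028 to 0.020 mm. If the total SD of the side difference were 1.0 mm (assumed), halving the component would cut variance by 0.148² / 2, about 1%. At 1 degree and 16 mm the cut would be 0.559² / 2, about 16%. All of this stands, and the gain is uncertain.

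A reader might infer that the reliability check is blind to registration error. It is not: superimposition was itself repeated, so rotation enters each repeated canine reading. With single-reading reliability 0.905, error is 0.095 of the variance. A 1 degree SD (0.244 to 0.314 mm per canine) then requires readings with an SD of at least 0.244 / √0.095 = 0.79 to 0.314 / √0.095 = 1.02 mm. What the check lacks is any statistic on the difference.

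A reader might also infer bias. Random allocation of side and coding of the digital models argue against that. Nor is every primary measure exposed, since the caliper reading does not use the rugae.

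Finally, averaging removes only error that differs between the two superimpositions. Impression, cast and scan error is common to both, and best fit on the same two meshes may return nearly the same answer.

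**Conclusion.** The point holds for the 3D-model measure only. Occlusal-plane rotation error adds in the MOP-minus-control difference, and the reported alpha does not determine how repeatable that difference is. This follows from geometry and from what the reliability check reports.

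The size rests on assumptions: SE about 0.03 mm at a rotation SD of 0.25 degree (17 mm) and 0.09 to 0.12 mm at 1 degree (14 to 18 mm), with n = 28. Best-fit matching may keep it at the low end. It would be tempting to conclude that a true MOP effect will be lost in this error. The documents do not support that: they give no rotation SD, no SD of the side difference and no target difference in mm, only a standardised effect of 0.8. This is an inexpensive gain in precision and a gap in reporting, not a flaw that invalidates the comparison.

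**What to change.** - Start with the six repeated models. If both canines were read each time, recompute the repeats as right-minus-left differences and report the repeatability SD in mm. Six models give only a rough estimate.
- Have the same examiner re-superimpose and re-measure every follow-up model once, picking the rugae points afresh and masked to the first reading.
- Analyse the mean of the two MOP-minus-control differences as a within-patient paired contrast. This replaces the independent-samples t-test for this measure, and the change should be stated openly.
- Report repeatability of that difference in mm, and confine the present reliability statement to canine displacement.

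The cost is examiner time on existing scans: 28 × 3 = 84 repeats, or 56 × 3 = 168 if the total of 56 means patients. No new visits or staff are needed. Averaging at most halves the variance from re-registration (SE to about 0.02 mm at 0.25 degree, 0.065 to 0.084 mm at 1 degree, n = 28). The caliper measure needs no change on this account.
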